## **Apparatus**

**Physiological Data Acquisition.** A computer installed with DATAQ data acquisition recording software controls a Coulbourn Instrument no. S75-01 High Gain Bioamplifier/Coupler in order to filter and amplify electrocardiogram (ECG) data, which is used to obtain heart-rate. A Schmitt trigger apparatus, including a #551-12 Dual Retriggerable One-Shot and CI #S21-06 Bipolar Comparator, will be used to detect an R wave during recording of ECG data. Participants will have three Ag/AgCl electrodes attached: one below the right clavicle, one below the left clavicle, and one on the left torso (i.e., below the rib cage) as a ground. The electrodes are equipped with adhesive ends and are filled with a NaCl .05 molar solution. Beats per minute (bpm) are transformed from the recorded interbeat intervals.

**Access to exposure materials.** The self-directed exposure will be provided to the participants via Qualtrics, which is an online website designed to conduct research. Qualtrics is available to use on mobile devices, which will be utilized by the researchers. The participants will be given an ID and password to log into Qualtrics, and the assigned IDs will be used to differentiate the participants. Before and after each exposure video, the participants will rate distress on the Subjective Units of Distress Scale (SUDS; Wolpe, 1973). Participants will complete the SUDS on their mobile phones that will be accessing the Qualtrics website. The rating of SUDS and participants' total time spent on each webpage will be collected and stored on Qualtrics, which will be available for the researcher to download at a later time. Participants will receive daily text messages as a reminder to conduct the exposure session.

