Participants in the treatment group will receive daily text messages as a reminder to conduct the exposure. Participants will be asked to follow the link and sign in each day with their mobile phones. Before each exposure video, the participants will rate expected distress on the SUDS. Then the participants will be asked to watch a video depicting dental care-related phobic material. After viewing the exposure video, participants will rate actual distress experienced on the SUDS. The participants will then be prompted to watch the video again. If the participant decides to view the video again, they will go through the same procedure of pre-rating fear and anxiety, watching the video, and post-rating fear and anxiety. Finally, the participants will be prompted to complete the procedure once more. After completing the procedure three times, the participants will no longer be prompted, however, they have the ability to complete the procedure two more times if they so desire.

The participants in the treatment group will be randomly assigned by previously prepared sealed opaque envelopes to video content (i.e., first- or third-person perspective). After 1-week of first or third video perspective, the participants will be assessed by the researcher via

telephone. Questions on the PQ and the DFS will be answered by the participants. After the assessment, participants in the first-person perspective will be informed that the video content will change to third-person perspective. Participants in the third-person condition will be informed that the video content will change to first-person perspective. At the end of the two weeks, participants will be asked to return in person for a follow-up and to receive \$40.00 compensation. The follow-up assessment will consist of the DBAT, completing the DFS, answering the PQ, and rating acceptability of using a mobile phone as a mean of self-directed exposure.

The control group will be assessed on the DFS after one week via telephone. After the two weeks the participants in the control group will be asked to return for a follow-up assessment and receive \$40.00 compensation. The assessment will consist of the same as the treatment group. At the follow-up session, participants in the control group will be offered the same treatment, for ethical reasons, as the experimental group, however, the data will not be analyzed.

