Proposed Analyses

Rates of procedure adherence (i.e., watching the video at least three times daily) will be assessed in order to examine the study's first question. The second question will be assessed by examining participants' rating of acceptability on the AARP with using a mobile phone as a method for self-directed exposure.

There will be 3 (group) x 2 (assessment) mixed measures analyses of variance (ANOVAs) which will be conducted to assess the first hypothesis regarding treatment effectiveness, with the DFS, and various DBAT measures (i.e., avoidance/escape, cardiac response, and SUDS verbal reports) as dependent variables. Sensitivity analyses will be conducted for baseline measurements. In order to examine the second hypothesis, a paired sample *t*-test assessing the relation of video perspective and scores on the PQ will be conducted.

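### The week-1 presence rating is taken by telephone by a researcher who is not masked to video perspective, and any resulting bias in the Hypothesis 2 comparison would not be removed by the randomised order

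*Protocol*

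**What the plan says.** After one week on the first assigned video, treated participants are contacted by telephone. The Procedure section of the Protocol says that "the participants will be assessed by the researcher via" telephone, and that "Questions on the PQ and the DFS will be answered by the participants". The change of video follows: "After the assessment, participants in the first-person perspective will be informed that the video content will change to third-person perspective", and "Participants in the third-person condition will be informed that the video content will change to first-person perspective". The starting perspective is randomised by sealed opaque envelope.

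The second presence rating is given at the in-person visit at two weeks. Whether it is written or read out is not stated.

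Hypothesis 2, in the Protocol's opening section, predicts greater presence with the first-person video. The SAP tests it with a paired t-test "assessing the relation of video perspective and scores on the PQ will be conducted", with no term for order, period, mode or interviewer.

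On the platform, the Apparatus section says that "Qualtrics is available to use on mobile devices, which will be utilized by the researchers". Treated participants already enter their distress ratings there by phone.

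**The concern.** Presence is a subjective rating on a Likert-type scale from 0 to 6. At week 1 it is given to a member of the research team, by telephone, and the plan does not say that this person is kept unaware of the video being rated. An interviewer who knows the condition and the hypothesis can influence such answers through tone, prompting or clarification, and a participant can lean towards what seems to be wanted.

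Randomised order protects the paired comparison against anything that belongs to the week or to the telephone. It gives no protection against an influence that depends on which perspective is being rated. That kind of influence would bias the only planned test of Hypothesis 2 in the hypothesised direction, and it could not be separated from a true perspective effect afterwards.

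**Working it through.** **Inputs.**
- From the documents: total sample size 36 (Participants); one presence rating per perspective per treated participant, the first by telephone and the second in person (Procedure); a paired t-test (SAP).
- Assumed: two-sided 5% level; order randomised 1:1; no true perspective effect. The number treated is not settled. Three equal groups of 12 would give 24 treated, and an equal split between waitlist and treatment would give 18, so both are shown.
- Assumed, because the documents give no figure: the size of any interviewer effect.

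**The plan's own figure.** The plan gives no number for Hypothesis 2 or for interviewer effects. The 36 itself can be reproduced with f = .25, three groups, two measurements, power .80, and an assumed alpha of .05 and correlation of .5. As a within-subject effect, this gives N = 36 with power .829. It is used here only to obtain the 18 and 24.

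**Step 1: bias by order.** Let the week-1 influence raise first-person ratings by e1 and lower third-person ratings by e3, both in SDs of the paired difference. Let m be a general telephone or period effect on week-1 ratings. The bias in first-minus-third is:
- first-person video first: e1 + m
- third-person video first: e3 − m

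With 1:1 orders the mean bias is b = (e1 + e3)/2, and m cancels.

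| Situation | First-person first | Third-person first | Mean |
|---|---|---|---|
| Telephone or period effect only, m = 0.3 | +0.3 | −0.3 | 0 |
| First-person raised only, e1 = 0.3 | +0.3 | 0 | 0.15 |
| Third-person lowered only, e3 = 0.3 | 0 | +0.3 | 0.15 |
| Both, e1 = e3 = 0.3 | +0.3 | +0.3 | 0.3 |

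If the symmetric influence in the last row also acted at the week-2 visit, the bias would be 0.6 in both orders.

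**Step 2: would a period term help?** A period-adjusted crossover analysis estimates the perspective effect as the average of the two order-specific mean differences. That average is [(e1 + m) + (e3 − m)]/2 = (e1 + e3)/2, the same bias. The period term absorbs m and half the difference between e1 and e3. It does not absorb their sum.

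**Step 3: effect on the error rate.** With true difference zero and bias b, the paired t statistic is treated as noncentral t with n − 1 degrees of freedom and noncentrality b√n. The critical values are 2.110 (n = 18) and 2.069 (n = 24).

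| b (SD of paired difference) | False first-person result, n = 18 | Either direction, n = 18 | False first-person result, n = 24 | Either direction, n = 24 |
|---|---|---|---|---|
| 0 | 2.5% | 5.0% | 2.5% | 5.0% |
| 0.05 | 3.9% | 5.5% | 4.2% | 5.6% |
| 0.1 | 5.9% | 6.9% | 6.8% | 7.6% |
| 0.2 | 12.3% | 12.6% | 15.4% | 15.6% |
| 0.3 | 22.4% | 22.5% | 29.1% | 29.1% |

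For example, at n = 24 and b = 0.3 the noncentrality is 0.3 × √24 = 1.47 and the upper-tail probability is .291.

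**Check by simulation** (40,000 runs, n = 24, 12 per order, shift 0.3): false first-person results were 29.5% when the shift was tied to perspective in both orders, 10.3% when it acted in one order only, and 2.0% when it was a pure telephone or period effect.

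**The case against.** Several points on the other side stand.

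- **Who knows what, and when, is not stated.** A reader might infer that the caller who records the answers also announces the switch, and so must know the perspective. The Protocol does not say this: participants are to be informed, but by whom, and whether in the same call, is left open. What the documents support is that no masking is described.
- **The announcement is already placed after the assessment.** News of the coming change therefore cannot colour the week-1 answers. The exposure is the caller's possible knowledge, not the timing of the announcement.
- **The bias need not fall in both orders.** A reader might infer that it always adds in both. That requires first-person ratings to be raised and third-person ratings lowered. If only one perspective is affected, the other order contributes nothing and the mean bias is halved, though it still does not cancel.
- **The size is assumed.** The questionnaire has fixed items and anchored responses, which limits an interviewer's room for influence. At b = 0.05 the inflation is small, and the overall two-sided error is only 5.5% to 5.6%. The 22% and 29% figures need 0.3 SD, for instance 0.3 in both directions.
- **The week-1 DFS is not part of this problem.** A reader might extend the point to it. But Hypothesis 2 is tested on presence only, the ANOVA has two assessments and does not clearly use the week-1 DFS, and controls also give that DFS by telephone. Caller knowledge of treatment group would be a separate matter, unrelated to video order.

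What does not stand is the suggestion that randomised order makes masking unnecessary. Step 1 of the working shows that it does not.

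**Conclusion.** The point holds as a vulnerability in data collection that can be avoided cheaply. It is not a demonstrated bias. One of the two ratings in every Hypothesis 2 pair is taken by a researcher for whom no masking to perspective is described. Any influence tied to perspective would bias the mean difference by (e1 + e3)/2, whatever the analysis does about period.

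Under the assumed range of 0.05 to 0.3 SD of the paired difference, the chance of a false first-person result is about 4-22% with 18 treated and 4-29% with 24, against 2.5%. These figures are illustrative. They rest on an assumed effect size, 1:1 orders, no true effect and a two-sided 5% test. The point concerns the second hypothesis only, and leaves the questions on use and acceptability and the treatment comparison untouched.

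**What to change.** In the Procedure section, have treated participants complete the week-1 presence questionnaire themselves on Qualtrics, through a link sent with the day-7 text. Use the same self-completed form at the week-2 visit and say so, since the mode there is not stated. Keep the telephone call for reminders and for announcing the switch, which already follows the assessment.

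If a presence questionnaire must be taken by telephone, for example from someone who has not submitted the form, use a caller who is unaware of the perspective until the answers are recorded.

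Moving the week-1 DFS to the same form is optional. If it is moved for controls too, they would need Qualtrics access and a prompt during the waiting period, because the daily texts and sign-in are described only for the treatment group.

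The cost is one protocol paragraph, one extra form and some reminder calls. No visits are added.

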## **Study Protocol**

The proposed study will examine the question of whether phobic individuals will use a mobile phone in self-directed exposure therapy. A second question is whether phobic participants will find the use of a mobile phone as an acceptable means of conducting self-directed exposure therapy.

Accompanying these two research questions are additional specific hypotheses. The first hypothesis is that filmed exposure stimuli, available on a mobile phone, will be associated with greater fear reduction in a self-directed exposure group relative to a control group. The second hypothesis is that greater presence will be reported with first-person perspective versus third-person perspective.

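### The paired test of presence (Hypothesis 2) cannot separate perspective from contrast, demand or carry-over after an announced switch without washout; the direction of any bias is unknown, and the week-1 comparison should be reported beside it

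*Protocol*

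**What the plan says.** The protocol's opening section gives Hypothesis 2 a direction: "The second hypothesis is that greater presence will be reported with first-person perspective versus third-person perspective".

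Under Procedure, treated participants are randomised by sealed envelope to begin with one perspective. After a week they answer the presence questionnaire (PQ, taken here to be the IPQ described under Self-Report Measures) and the DFS by telephone. The researcher then tells them what comes next. For one order: "After the assessment, participants in the first-person perspective will be informed that the video content will change to third-person perspective". For the other: "Participants in the third-person condition will be informed that the video content will change to first-person perspective".

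The second perspective fills the remaining week, and no washout is described: "At the end of the two weeks, participants will be asked to return in person for a follow-up". The second presence rating belongs to that visit: "The follow-up assessment will consist of the DBAT, completing the DFS, answering the PQ, and rating acceptability".

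The SAP (Proposed Analyses) plans one analysis for this hypothesis: "a paired sample *t*-test assessing the relation of video perspective and scores on the PQ will be conducted". It mentions no order, period or carry-over term and no comparison restricted to the first week.

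**The concern.** The two presence ratings are not made under the same conditions. The week-1 rating comes from someone who has used only one video in the study and has not yet been told of a switch. The week-2 rating comes from someone who has just used the other video and has been told which perspective follows. Three things could move the second rating:

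- **Contrast:** the second video is judged against the first.
- **Demand:** the participant sees that perspective is the manipulated feature and answers accordingly.
- **Carry-over by assimilation:** the second answer is drawn towards the first.

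The usual defence of a crossover is that randomised order cancels whatever changes between periods. That covers a change common to both orders, such as habituation or the move from telephone to in-person rating. It does not cover a shift that depends on which video came first. The paired test averages affected and unaffected ratings, so a positive result could be partly artefact and a null result could hide a real difference. Nothing in the planned output would show either.

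**Working it through.** **Inputs.** The plan gives no sample size, shift or correlation for Hypothesis 2. Its total of 36 (Participants) was derived for the three-group, two-measurement design and is used here only to obtain the number treated. All of the following are assumptions:

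- Treated n = 24 if the three groups are equal (36 × 2/3), or 18 if waitlist and treatment are 1:1 (36/2).
- The two orders are equal in size (12 or 9 each).
- Rating SD is 1 and within-person correlation 0.5, so the SD of a paired difference is √(2 × (1 − 0.5)) = 1.
- Two-sided alpha is .05.

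**Step 1: what the paired mean estimates.** Let δ be the true first-minus-third difference and π a week-2 shift common to both orders. Let c_A and c_B be the order-specific shifts in the first-minus-third difference.

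- First-person then third-person: expected difference = δ − π + c_A
- Third-person then first-person: expected difference = δ + π + c_B
- Mean over equal orders = δ + (c_A + c_B)/2

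So π cancels. Shifts of opposite sign (+0.2 and −0.2) also cancel. Shifts of the same sign do not: c in both orders gives a bias of c. Balance matters for π: with 15 and 9 per order and π = 0.3, the bias is −0.3 × (15 − 9)/24 = −0.075 (simulated −0.073).

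**Step 2: shift towards first-person, no true difference.** The noncentrality parameter is c√n, and rejection comes from the noncentral t with n − 1 df.

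| Assumed shift (SD) | n = 24 | n = 18 |
|---|---|---|
| 0 | 5% | 5% |
| 0.2 | 15.6% | 12.6% |
| 0.3 | 29.1% | 22.5% |
| 0.5 | 65.0% | 51.6% |

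**Step 3: shift the other way.** Suppose the second rating is drawn towards the first by 0.2 SD in both orders. With n = 24, a true difference of 0.5 SD becomes 0.5 − 0.2 = 0.3 SD. Power falls from 65% to about 29%.

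**Step 4: would a model term repair it?** No. The week-1 between-order difference has expectation δ, and the week-2 one δ + c_A + c_B. The paired mean is their average. Adding period and sequence terms leaves the within-person estimate unchanged under equal orders, because the order-specific shift is aliased with sequence.

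**Step 5: what week 1 alone can offer.** It precedes any use of the other video, so it is free of contrast and carry-over from it. The 95% half-width is t(.975, 2m − 2) × √(2/m) for m per order:

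- m = 12: 2.074 × 0.408 = 0.85 SD
- m = 9: 2.120 × 0.471 = 1.00 SD

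Power at a true difference of 0.5 SD is 0.22 and 0.17 respectively, against 0.65 for the paired test with 24.

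**Step 6: should week 1 act as a gate?** One could call Hypothesis 2 supported only if the week-1 estimate has the same sign. Simulated with n = 24 and no true difference, false positives at shifts of 0.2, 0.3 and 0.5 SD fall only to about 12%, 21% and 40%, because the week-1 ratings are half of the paired data. Power at a true 0.5 SD falls from 65% to about 62%. The rule does not protect the conclusion.

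**The case against.** A within-person comparison in randomised order is a conventional choice, and it is far more efficient than the between-person alternative. The common period effect, including the change from telephone to in-person rating, does cancel if the orders are balanced. Presence is one of the additional hypotheses; use and acceptability come first. All of this stands, and it is why the paired test should stay.

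A reader might infer that contrast and demand push both orders towards first-person, so that the planned test is inflated. The documents do not support that. They give no sign or size for any shift. Demand in that direction requires participants to guess the hypothesis, and nothing says they are told it. The announcement names the next perspective, not the expected result, and the perspective is plain once the video plays. A missing washout is no reason to prefer inflation, since assimilation would shrink the difference.

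It would also go too far to call the week-1 ratings free of all demand. They precede the switch, but the protocol does not say whether both perspectives are disclosed at entry, and the consent pages are not in the text reviewed.

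What survives is narrower: counterbalancing does not deal with order-specific effects, and the plan omits the one estimate that precedes the switch.

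**Conclusion.** The concern holds as an ambiguity of unknown direction, not as a demonstrated bias. The paired contrast estimates the perspective effect plus the mean of two order-specific shifts that the plan can neither remove nor display. The false positive range of about 16% to 65% (13% to 52% with 18 treated) and the loss of power from 65% to about 29% are illustrations. They rest on the assumed shifts, the correlation of 0.5, alpha .05, equal orders and the assumed number treated. They show that moderate shifts would matter in either direction, not that such shifts will occur. This is an optional, low-severity improvement.

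**What to change.** 1. **Protocol, Procedure.** Word the switch announcement neutrally, saying that a different video follows without naming its perspective. This only reduces cueing, because the change is visible in the video, and it does nothing about contrast. Cost: one sentence in the telephone script.

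2. **SAP, Proposed Analyses.** Keep the paired analysis. Add, as a sensitivity analysis, the week-1 PQ difference between participants randomised to first-person and to third-person video, with its 95% CI. Describe it as free of carry-over and contrast from the other video, though not necessarily of all demand. If the two estimates diverge, describe the paired result as possibly affected by contrast, demand or carry-over. Cost: one extra estimate from data already collected.

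3. **No gate.** Do not make support for Hypothesis 2 depend on the sign of the week-1 estimate.

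The SAP should state the limitation: with a half-width of about 0.85 SD (12 per order) to 1.0 SD (9 per order), the week-1 estimate is a descriptive check with little power to reveal moderate carry-over, and agreement between the two estimates is not evidence that there is none.

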#### **Abbreviated acceptability rating profile (AARP; Tarnowski & Simonian, 1992).**

The AARP consists of 8-items that assess acceptability of treatment. Refer to appendix E. Items are rated on a 6-point Likert-type scale ranging from 1 (*strongly disagree*) to 6 (*strongly agree*). Good psychometrics have been demonstrated with the AARP (Cronbach's alpha ranging from .93 to .97; Caporino & Karver, 2012; Tarnowski & Simonian, 1992). The AARP was slightly modified to fit the current study.

**Dental Behavior Avoidance Test (DBAT).** In a laboratory furnished to exemplify a dental operatory, the DBAT will be conducted, consistent with prior research by McNeil, McGlynn, Cassisi, and Vrana (1989). The DBAT will consist of eight steps that simulate a dental examination, and each step will last up to 60 seconds. Escape from, or avoidance of, each step will be allowed, and will constitute a measure of escape/avoidance (i.e., total number of seconds of escape/avoidance behavior). A researcher will portray the dentist, and an undergraduate research assistant will portray the dental assistant. A maximum-distress SUDS rating will be reported by the participants at the end of each step of the DBAT. Throughout the procedure, participants' heart rate will be measured using a computer that controls a Coulbourn Instrument to measure ECG data. A four minute baseline will be recorded prior to the start of the DBAT. Before initiating the next step in the procedure, there will be a 60 second baseline recording.

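### Acceptability is rated only at the two-week in-person visit, so treated participants who do not return give no rating, and the plan could not detect a resulting bias

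*Protocol*

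**What the plan says.** The protocol's opening section sets the question: "A second question is whether phobic participants will find the use of a mobile phone as an acceptable means of conducting self-directed exposure therapy". The SAP's whole plan for it is that "The second question will be assessed by examining participants' rating of acceptability on the AARP". The SAP does not say whose ratings count or how people without a rating are handled. The only sensitivity analyses it names concern baseline measurements.

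The Procedure section fixes the timing for the treatment group:

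- At the week-1 telephone assessment: "Questions on the PQ and the DFS will be answered by the participants". Acceptability is not listed.
- At two weeks: "At the end of the two weeks, participants will be asked to return in person for a follow-up". That visit's content is: "The follow-up assessment will consist of the DBAT, completing the DFS, answering the PQ, and rating acceptability of using a mobile phone".

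The Apparatus section says that Qualtrics stores distress ratings and page times; it mentions no acceptability item. Neither document gives an expected drop-out rate, a withdrawal procedure or a missing-data plan.

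The control group's follow-up is described as matching the treatment group's: "The assessment will consist of the same as the treatment group". Whether waitlist participants should rate a method they have not yet used is a separate matter. This point concerns treated participants only.

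**The concern.** Acceptability is one of the study's two headline questions, and its answer comes from a single rating that exists only for those who attend one visit. Attendance could be related to what is being rated. Participants are recruited because they report discomfort with dental care. The ideal schedule is three viewings a day of a 15-minute video, or 45 minutes. The visit takes place in a room furnished as a dental operatory and repeats the simulated examination (DBAT). Someone who found the exposure hard to tolerate might be less willing to come back.

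If so, the mean AARP score would describe those who stayed but be read as describing everyone who was offered the method. In a study of about 36 people, a handful of missing ratings could move that mean noticeably. A rating that was never collected cannot be recovered at analysis.

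**Working it through.** **Where a rating can be obtained (treatment group)**

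| Contact | Mode | Collected | Acceptability? |
|---|---|---|---|
| Daily sessions | Phone, Qualtrics | Distress ratings, page time | No |
| Week 1 | Telephone | PQ, DFS | No |
| Week 2 | In person | DBAT, DFS, PQ, acceptability | Yes |

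Nothing in the Procedure makes the week-2 visit conditional on having watched the video. The rating is lost by missing the visit, not by stopping viewing.

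**The plan's own figures.** The documents give no figure for acceptability or drop-out, so there is none to reproduce on this point. The stated total of 36 is used below only to set the number treated.

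**Inputs**

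- From the protocol: at least 36 participants in three groups; AARP of 8 items, each scored 1 to 6, so the total runs from 8 to 48.
- Assumed: equal groups, with the two perspective orders forming the treated arm, so n = 36 × 2/3 = 24.
- Assumed: returners' item mean 5.0; non-returners would have averaged between 1 and 3; 2, 5 or 7 of the 24 do not return.

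**Formulas.** With d lost and non-returner mean m:

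- all-treated mean = [(24 − d) × 5.0 + d × m] / 24
- overstatement = 5.0 − all-treated mean = (d/24) × (5.0 − m)

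| Lost | All-treated mean, m = 1 | All-treated mean, m = 3 | Overstatement per item | On the 8 to 48 total (× 8) |
|---|---|---|---|---|
| 0 | 5.00 | 5.00 | 0 | 0 |
| 2 | (110 + 2)/24 = 4.67 | (110 + 6)/24 = 4.83 | 0.17 to 0.33 | 1.3 to 2.7 |
| 5 | (95 + 5)/24 = 4.17 | (95 + 15)/24 = 4.58 | 0.42 to 0.83 | 3.3 to 6.7 |
| 7 | (85 + 7)/24 = 3.83 | (85 + 21)/24 = 4.42 | 0.58 to 1.17 | 4.7 to 9.3 |

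**Without assuming who leaves.** If missing ratings could lie anywhere from 1 to 6, the possible range of the all-treated mean is 5 × d/24 wide: 0.42 points with 2 lost, 1.04 with 5 and 1.46 with 7, on a scale that spans 5 points.

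**A different split.** The Procedure describes assignment to waitlist or treatment. If that were one to one, 18 would be treated. With 4 of 18 lost, the overstatement is (4/18) × 2 = 0.44 to (4/18) × 4 = 0.89, similar to 5 of 24.

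**The case against.** Rating a treatment once, after it ends, is an ordinary design choice, and several features of this study work against loss. The $40 is paid at the follow-up visit, so the incentive attaches to attending rather than to viewing. Escape from or avoidance of any DBAT step is allowed, and participants have already been through one DBAT at baseline. Someone who dislikes the videos, stops early and returns still gives a rating. All of this stands, and it makes heavy loss less likely without ruling it out.

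People may also fail to return because of travel, time or dental fear unrelated to the phone method. That stands too. A reader might infer that acceptability will be biased upwards. The documents do not support so firm a statement, because they give neither a drop-out rate nor reasons for leaving. Upward bias needs both some loss and non-returners who are less accepting.

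Finally, adherence, Qualtrics records and the week-1 DFS and PQ would allow returners and non-returners to be compared on other measures. That is useful, but none of these is an acceptability rating. They can show disengagement; they do not show what the person thought of the method.

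**Conclusion.** The point holds in conditional form. As written, the plan obtains no acceptability rating from any treated participant who misses the two-week visit. If those participants are less accepting than returners, the reported result will be too high. Beyond the limits of the scale itself, the plan holds nothing with which to detect or bound the difference.

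Under the assumptions stated, the overstatement runs from 0.17 item points (2 of 24 lost, non-returners averaging 3) to 1.17 (7 of 24 lost, averaging 1). It is zero if everyone returns. No value in that range has special standing, because the loss and both means are assumed. A reader might also infer that anyone who gives up on the videos drops out of the acceptability result. The Procedure does not say that; only non-attendance has this effect.

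The change is worth making because it is cheap and must be in place before data collection.

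**What to change.** **Protocol, Procedure**

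- Add the eight-item AARP to the treatment group's week-1 telephone assessment, before the change of perspective is announced.
- Offer the week-2 AARP by telephone or Qualtrics to treated participants who do not return, and record how each rating was obtained.

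**SAP**

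- State that research question 2 is answered in treated participants, with the week-2 AARP as the main summary.
- Report how many treated participants lack a week-2 rating.
- Compare week-1 scores of returners and non-returners.
- Show a sensitivity summary that uses the week-1 score where week 2 is missing, labelled as such. Do not pool the two time points in the main result.

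**Cost.** A few minutes on a call already scheduled, a remote form for non-returners and one extra table. Sample size and treatment are unaffected. A week-1 rating reflects one week and one perspective, so it is an imperfect stand-in for week 2. Anyone lost before the call who also declines a remote rating is still missing.
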